Participants accessed the experiment via a Qualtrics link. They were provided detailed information about the study (see "Participants Information Sheet" included in the IRB package, https://osf.io/6w2zm/) and were then asked to provide consent prior to participating. Each participant was asked to take part in the survey using a smartphone with headphones or earphones attached, not a computer or laptop, because one experimental condition includes mindful walking and, participants being randomly allocated to conditions, we needed to ensure that everyone would be equally capable to perform the mindfulness activity. To know if this condition was verified we included a question in which we asked participants whether they started the survey from a device other than a smartphone; if they answered negatively,

we asked them to exit the survey and to restart it, this time using a smartphone with headphones or earphones attached.

Participants were also asked to sit in a quiet place such as a room where they could not be disturbed for 20 minutes. After providing informed consent, they were asked to complete the Neuroticism subscale of the IPIP - 5 NEO Domains (IPIP, 2021) to assess the level of neuroticism. Examples of items were "I often feel blue" or "I am filled with doubts about things". Participants could answer a 5-points scale (1 = *Very inaccurate*, 2 = *Moderately Inaccurate*, 3 = *Neither Inaccurate nor Accurate*, 4 = *Moderately Accurate*, 5 = *Very Accurate*). We estimated the scale reliability (i.e., internal consistency) using the omega coefficient. Assuming a unitary-factor model, the reliability estimate in the present sample was $\omega_u = x$.

After the completion of the neuroticism measure, participants were randomly allocated to one of the five conditions⁶. In each condition, participants were presented with a different 15-minutes recording. The four audio files of the mindfulness exercises and the three audio files of the stories of the non-mindful active control condition were recorded by a certified meditator, to keep the voice constant across conditions. Following a brief description of the mindfulness conditions and of the three different stories of the non-mindful active control condition.

Body scan. In body scan, participants were invited to "scan" their parts of the body. Every time the mind wandered, participants were invited to bring back the awareness and the attention to the part of the body they were "scanning".

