We decided to set a series of rules to deal with careless or insufficient effort responders (C/IE; Currant, 2016), to reduce errors and provide more valid results. We decided to be conservative in our criteria by excluding participants that were providing too unrealistic answers that can hardly be due to casual errors, but at most to a consistent pattern in the response modality (i.e., finishing the survey as soon as possible to get payments/credits). Some possible issues were limited by some settings we fixed in the Qualtrics survey; we forced the answers for the questions connected to our exclusion criteria (meditation experience, english level, mental illnesses) for the questionnaires related to our dependent variables/moderator instead the answers were requested¹⁰.

To be sure that participants listened to the 15 minutes mindfulness/control condition we blocked the screen with the audio of the meditation/ control condition for 14 minutes (i.e., 840 seconds) so as not to allow participants to proceed to the following survey page until the meditation was actually finished. However, we excluded participants that completed the survey in less than 946 seconds, because as in addition to the 15 minutes of the recording we added a cut score for response time at 2 seconds an item, by following the recommendations of Huang et al., (2012)¹¹ To exclude participants that provided the same response to every question (i.e., selecting always the answer "strongly agree") we performed a long string analysis. Here we followed the recommendations of Huang et al., (2012) and we excluded from the study individuals with a string of consistent responses equal or greater than 10 (i.e., half of the length of the total scale). Furthermore If a participant responded to less than 50% of the items on a scale, we excluded that participant's score for that scale. Finally we decided not to exclude outliers as we believe that this would have led to the loss of important information and we did not perform any transformation of the data.

Ethics Information, Administrative Organization and Data protection

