The study received ethical approval from Swansea University while the sites that participated in the data collection received ethical approval from their local IRBs. To minimize the workload to collaborators, we provided an IRB submission pack that sites could adapt to their institutions' requirements. For most sites, only small adjustments to our IRB pack were necessary for submission. Each site's IRB protocols with ethics details and acceptance of each protocol can be found on the OSF project page at https://osf.io/6w2zm/.

¹⁰If participants do not provide any answer a message appears asking participants whether they want to continue to the following part of the survey without answering that particular question.

¹¹ We had 53 questions resulting in 103 seconds to be added to the 840 seconds of the meditation/control condition thus arriving at 946 seconds

Swansea University was the administrative organization for the study. Swansea University was also the data controller for this project. Personal data of participants were processed for the purposes outlined in the information sheet (see the document Information Sheet at https://osf.io/xuznc/). Standard ethical procedures involved participants providing their consent to participate in this study by completing the consent form that was administered at the beginning of the online survey used for the experiment.

We left each site the possibility to recruit participants in their preferred way. Participants could be recruited through the SONA system of the respective institution or via crowdsourcing platforms such as mTurk or Prolific academic. Participants could come from any geographic area if they met our inclusion criteria and could be given either credits or financial compensation in exchange for participation in the study.

Conflict of interests

The certified mindfulness instructor that collaborated on the multi-site project only recorded the meditations, but was not involved in the writing of any parts of the manuscript (e.g., choice of the analyses).

References

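### The 2-seconds-per-item speed check is run on whole-survey time, so it does not enforce 2 seconds per item

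*Combined protocol and SAP*

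**What the plan says.** The rule is in the section on careless or insufficient effort responders. The standard is stated per item: "we added a cut score for response time at 2 seconds an item". The test is on the survey as a whole: "we excluded participants that completed the survey in less than 946 seconds". Footnote 11 gives the build-up: "We had 53 questions resulting in 103 seconds to be added to the 840 seconds of the meditation/control condition thus arriving at 946 seconds".

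Four other statements bear on what that total contains:

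- The same section locks the audio page for 840 s and states no maximum time on it.
- The recording is longer than the lock. Procedure says that "participants were presented with a different 15-minutes recording", and the rule itself describes the item allowance as coming "in addition to the 15 minutes of the recording".
- Study information and consent fall inside the survey. Procedure puts both after the Qualtrics link is opened, and the ethics section describes participants "completing the consent form that was administered at the beginning of the online survey used for the experiment".
- Allocation precedes the audio page and the outcome scales: "After the completion of the neuroticism measure, participants were randomly allocated to one of the five conditions".

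No page-level or item-level timing is described for this check. Two other data-quality rules sit beside it: exclusion for a run of 10 or more identical responses, and removal of a scale score when fewer than half of its items are answered.

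**The concern.** The quantity tested is not the quantity in the stated standard. A total-time threshold equals a per-item threshold only if everything else in the total is fixed and fully deducted. Here the plan deducts the 840 s lock and nothing more. Each second on information, consent or the unlocked audio page relaxes the pace demanded on the items, by an amount that varies between participants.

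The rule is aimed at people who hurry to the end for pay or credit, and recruitment through crowdsourcing platforms and course-credit systems makes that a realistic risk. Any such records that are kept enter the Bayes factors that decide when each comparison stops and where later participants are allocated. In addition, much of the time being measured comes after allocation, so who is excluded depends partly on behaviour that the assigned exercise might influence.

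**Working it through.** **Inputs.** Cut-off 946 s, standard 2 s per item and lock 840 s (section on careless responders); 53 questions (footnote 11); recording 15 min = 900 s (Procedure and the rule itself); 20 state anxiety items (Procedure). Time on information and consent is not given, so it is varied as an assumption.

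**Step 1. Reproduce the cut-off.** 840 + 2 × 53 = 840 + 106 = 946 s, which matches. The footnote's printed 103 s would give 840 + 103 = 943 s, so 103 is a slip for 106.

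**Step 2. Pace actually enforced.** With A seconds on the audio page and T seconds on everything else that is not an item, the enforced minimum is max(0, 946 − A − T)/53 seconds per item.

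| Audio page, A | Other time, T (assumed) | Left for 53 items | Enforced minimum per item |
|---|---|---|---|
| 840 s | 0 s | 106 s | 2.00 s |
| 840 s | 30 s | 76 s | 1.43 s |
| 840 s | 60 s | 46 s | 0.87 s |
| 840 s | 90 s | 16 s | 0.30 s |
| 840 s | 106 s | 0 s | 0 |
| 900 s | 0 s | 46 s | 0.87 s |
| 900 s | 15 s | 31 s | 0.58 s |
| 900 s | 30 s | 16 s | 0.30 s |
| 900 s | 46 s | 0 s | 0 |

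The 2 s standard is met only in the first row. The row with A = 900 and T = 0 needs no assumption about reading time. The gap between lock and recording (900 − 840 = 60 s) uses 60/106 = 57% of the item allowance, and that time is listening, not idling.

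**Step 3. Would a different cut-off cure it?** Building the floor on the full recording gives 900 + 106 = 1006 s. A full listener with T = 60 s is then still held to only (1006 − 900 − 60)/53 = 0.87 s per item. Someone who leaves the page at 840 s with T = 0 is held to (1006 − 840)/53 = 3.13 s, which is stricter than intended. No single total gives 2 s per item for both.

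**Step 4. Position relative to allocation.** At the cut-off, at least 840 of the 946 s (840/946 = 89%) is spent on the audio page, after randomisation. The state anxiety and manikin items also follow it.

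**The case against.** The strongest reply is that the rule is meant to be lenient. The authors say that they want conservative criteria and are after people racing to the end. Such a person leaves the audio page near 840 s and skims the consent pages, which is where the rule comes closest to 2 s per item. The other two rules also do some of the work: tapping one option down the 20-item state anxiety scale triggers the long-string exclusion, and skipping more than half of a scale removes its score. This stands as a limit on severity. It does not rescue the rule, because fast, varied tapping passes the long-string check, and someone who hears the whole recording is outside the 2 s standard before any consent time is counted.

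Three stronger readings are tempting, and the documents support none of them.

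- *Most careless responders stay in, with a calculable loss in the chance of reaching the H1 boundary.* Any such figure needs the share of random responders who pass this rule but would fail a better one. The documents give nothing on that. Comparing contaminated with clean data would not measure the difference between the two rules.
- *The rule biases the comparison between arms.* The lock and cut-off are identical in all five conditions, and no figure shows that time on the audio page differs by arm. Mindful walking makes a difference conceivable, no more. If the floor is near zero for most people, few are excluded and selection by arm is correspondingly small. Nor is the whole-survey clock the sole cause: timing the outcome pages would also be post-allocation.
- *Someone can idle after the page unlocks and then tap through all 53 items.* The neuroticism items come before the audio page, so that sequence cannot occur. What remains is that idle time offsets fast answering anywhere in the total.

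**Conclusion.** The point holds as a mismatch between the stated standard and the clock used to apply it. The enforced minimum is 0.87 s per item for a participant who hears the full 15 minutes, and lower once information and consent are counted. It is zero from 46 s of such time for that participant, and from 106 s for one who leaves at 840 s. The 0.87 s figure uses only printed numbers; the points at which it reaches zero depend on assumed reading times. The plan does not name the timing variable, but its wording, with consent at the start of the same survey, points to whole-survey duration.

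The consequence is under-exclusion of fast responders with varied answers. Its effect on the estimates or Bayes factors cannot be derived from the documents. Differential exclusion by arm is possible but not shown. Severity is minor to moderate.

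**What to change.** 1. Replace the whole-survey floor with the 2 s per item rule applied to Qualtrics page timers on the questionnaire pages: 2 × 53 = 106 s over all items, or 2 × 20 = 40 s for the state anxiety scale alone. State which pages make up the 53 questions.
2. Report the number excluded for speed in each arm.
3. Add a sensitivity analysis that either excludes only on the neuroticism page, which is completed before randomisation, or keeps all randomised participants with outcome data. Making the neuroticism page the only screen in the confirmatory analysis would remove dependence on arm, but it would leave the primary outcome with no speed check. That trade-off is better placed in a sensitivity analysis.
4. Correct 103 s to 106 s in footnote 11, and reconcile the 15 minutes named in the text with the 840 s used in the sum.

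The cost is hidden timing questions in the survey, one revised paragraph and somewhat more exclusions. The timers have to be in place before collection begins. If page times were not recorded, the exclusions by arm and the analysis keeping all randomised participants with outcome data can still be reported.
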